**Specific Aim #1. Determine the effectiveness of iNO therapy on improving neurodevelopmental outcome in all O2-dependent premature infants having birth weights < 1500g.** We hypothesize that iNO therapy will improve neurodevelopmental outcome and growth at 18 months postconceptional age compared with placebo treated infants. In a double-blind, placebo-controlled clinical trial, premature infants being cared for in the Intensive Care Nursery at the University of Chicago Medical Center requiring any level of respiratory support will be randomized to receive iNO or placebo gas. Treatment will continue until infants either no longer require supplemental O2 therapy or reach 33 weeks gestational age, whichever comes first. At 18 months postconceptional age, infants will have neurodevelopment assessed and secondary clinical outcomes measured. The relative risks of abnormal neurodevelopmental outcome in the two groups will be compared. The roles played by variables known to independently affect neurodevelopmental outcome, as well as variables known to mediate abnormal neurodevelopmental outcomes will be statistically assessed.

**Specific Aim #2. Assess the mechanisms by which iNO therapy alters neurodevelopmental outcome in preterm infants.** We hypothesize that the amount of nitric oxide delivery to tissues will be positively correlated with neurodevelopmental outcome. Using routinely collected arterial and venous blood from infants in this study, measurements of nitrosylated hemoglobin and nitrite will be made. Arterial-venous differences will be calculated and mean differences compared across treatment groups. Arterial venous

differences will be regressed against neurodevelopmental outcome. Plasma levels of cyclic guanosine monophosphate (cGMP), the intracellular second messenger induced by nitric oxide will also be measured and levels regressed against neurodevelopmental outcome.

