#### **4. What are the mechanisms by which iNO therapy alters neurodevelopmental outcome in preterm infants?**

In studies of brain injury in animals, nitric oxide (NO) has been associated with neuroprotection, mostly likely through actions on the blood vessels of the brain. After inhalation, iNO crosses the alveoli (air sacs) of the lung and enters the circulation, where it is bound to hemoglobin. It had been believed that NO bound to hemoglobin was inactivated. How, then could inhaled NO be delivered to target tissues, such as the brain? New data indicate that hemoglobin may act as a delivery system for NO to target tissues. Neuroprotection may be due to actions of NO on blood vessels in the brain, with its ability to increase blood flow to injured areas of the brain.

In the laboratory component of this study, we propose to measure NO metabolites in the blood of our study babies treated with iNO or placebo. Recent data now suggest that NO, both administered as well as naturally

produced, is transported in blood to target tissues, where it can increase local blood flow. This has been documented in humans, where inhalation of NO was found to increase blood flow in the arm of exercising volunteers. Furthermore, NO has been shown to be carried on the hemoglobin molecule in red blood cells – the hemoglobin becomes nitrosylated, carrying an NO molecule. Thus, iNO markedly elevates levels of total nitrosylated hemoglobin in human volunteers. Most importantly, there is a marked difference in the amount of nitrosylated hemoglobin between the arterial circulation carried to the tissues, and the venous circulation carried away from the tissues. This difference indicates that inhaled NO delivered in the arterial blood is being removed from hemoglobin in the tissues, consistent with its effect in organ capillary beds. In addition to nitrosylating hemoglobin, plasma nitrite also appears to be a source of bio-available NO. Nitrite, generated from the reaction of NO with oxygen, can be converted back to NO by means of naturally occurring enzymes in the body. In fact, similar to levels of nitrosylated hemoglobin, large differences in arterial and venous nitrite levels have been documented in humans, and has been shown to be bioactive.

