### **Specific Aim #2. Assess the mechanisms by which iNO therapy alters neurodevelopmental outcome in preterm infants.**

(i) *Rationale.* We have previously found that iNO therapy reduces the risk of abnormal neurodevelopmental outcomes independently of the level of prematurity or complications of prematurity known to affect neurodevelopmental outcome. Therefore, it appears that iNO has direct, beneficial effects on the preterm brain and its response to the stress of existence outside the womb. Previously, iNO was believed to be inactivated in the blood vessels in the lung, by binding to hemoglobin in the blood. However, there is increasing evidence that hemoglobin binding does not inactivate NO permanently, but rather transports it for delivery to target tissues. The goal of this Specific Aim, therefore, is to assess the amount of delivered NO that is transported to our patients' tissues, measure the amount of NO activity in our patients' blood, and examine the relationships between these measures, the iNO concentrations administered, and the patients' neurodevelopmental outcomes.

(ii) *Study Design.* Measurements of nitrosylated hemoglobin from arterial and venous blood samples will be made on each patient at defined points during the hospitalization: in the first 48 hrs following initiation of study gas (iNO or placebo), after 1 week of treatment, after 2 weeks of treatment. In infants who are treated longer than 2 weeks (anticipated to be all infants born before 31 weeks gestation, since they will likely still require some respiratory support), weekly measurements of venous nitrosylated hemoglobin will be made. Cyclic GMP will be measured once, after 1 week of therapy. For each patient, arterial and venous values will be compared, to identify the amount of NO that is delivered to tissues, and these values plotted over time. Mean delivered amounts will be compared across treatment groups, and individual values correlated with neurodevelopmental outcome. Cyclic GMP levels, a measure of nitric oxide activity, will be averaged within groups and treatment groups compared.

(iii) *Source of blood.* This protocol does not require for blood draws outside the regular scope of practice. Samples will be taken from regularly scheduled arterial and venous draws, and leftovers from these samples used.

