(vii) *Data Analysis.* Arterial-venous differences in S-nitroso-hemoglobin and plasma nitrite levels will be calculated on a patient-by-patient basis. Mean levels within groups will be compared across groups, and statistical significance tested with ANOVA. Individual values of A-V differences will be compared with neurodevelopmental outcome on a patient-by-patient basis and assessed with regression techniques. Similar analyses will be performed with cGMP values.

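### Aim 2 names no treatment term or covariates for relating NO delivery to outcome, so a pooled association cannot on its own be read as mechanism

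*Combined protocol and SAP*

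**What the plan says.** Aim 2 is one of the trial's two aims and is titled as an assessment of mechanism. Its hypothesis, in Specific Aims, is that "the amount of nitric oxide delivery to tissues will be positively correlated with neurodevelopmental outcome".

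Both arms are sampled. Background section 4 says "we propose to measure NO metabolites in the blood of our study babies treated with iNO or placebo".

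The link to outcome is described in three places:
- Specific Aims: arterial-venous (A-V) "differences will be regressed against neurodevelopmental outcome", and plasma cGMP is treated the same way.
- Specific Aim #2 (ii), Study Design: "Mean delivered amounts will be compared across treatment groups, and individual values correlated with neurodevelopmental outcome".
- Specific Aim #2 (vii), Data Analysis: "Individual values of A-V differences will be compared with neurodevelopmental outcome on a patient-by-patient basis and assessed with regression techniques". A further sentence extends this to cGMP.

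Treatment group is used only to compare mean levels (by ANOVA in (vii)). The nearest thing to a treatment variable in the outcome analysis is in the rationale, Specific Aim #2 (i), whose goal is to "examine the relationships between these measures, the iNO concentrations administered" and the outcomes. Section (vii) contains no model that uses those concentrations.

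**The concern.** Two arm differences are expected by design. Background section 4 reports that inhaled NO raises total nitrosylated hemoglobin in volunteers, and the sample size section plans on abnormal outcome falling from 40% to 20%. When treatment moves both the marker and the outcome, the two are correlated across all infants whether or not one acts through the other. The pooled slope then mixes the arm contrast with any genuine link between delivery and outcome.

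Under an Aim titled as mechanism, a significant pooled slope could be reported as support for NO delivery to tissue as the route of benefit, when it may only restate the Aim 1 treatment effect.

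Covariates matter too. Background section 1 says adverse outcomes become more frequent with greater prematurity, and the Treatment section ties duration of gas to gestational age and oxygen need. The Aim 1 analysis lists birth weight, sex and socioeconomic status for adjustment; the Aim 2 analysis lists nothing.

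**Working it through.** **1. The plan's own figure.** Aim 2 has no sample size of its own, so the Aim 1 size is used. For 40% v 20%, 80% power and an assumed two-sided alpha of 0.05 (not stated in the sample size section), with a pooled-variance test:

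n per arm = [1.96·√(2·0.30·0.70) + 0.8416·√(0.40·0.60 + 0.20·0.80)]² / 0.20² = 81.2, rounded up to 82.

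This matches the stated 82 per arm, 164 in total.

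**2. Set-up.** Let A be the arm (0 placebo, 1 iNO; 1:1) and Y abnormal outcome, with probability 0.40 − 0.20·A. Let the marker be M = d·A + e, where e is normal with SD 1 and independent of Y within each arm. The separation d, in within-arm SDs, is not given in the documents, so it is varied.

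**3. Expected pooled association.**
- Cov(M, Y) = d·Var(A)·(−0.20) = d·0.25·(−0.20) = −0.05·d
- Var(M) = 1 + 0.25·d²
- Var(Y) = 0.30·0.70 = 0.21
- r = −0.05·d / √[(1 + 0.25·d²)·0.21]

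With 164 infants, |z| ≈ |r|·√162 / √(1 − r²), and the chance of significance is about Φ(|z| − 1.96). For d = 2: r = −0.10 / √(2·0.21) = −0.154, |z| = 1.99, and Φ(0.03) = 51%.

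**4. Simulation.** Logistic regression of outcome on marker, Wald test at two-sided 0.05, 5,000 trials per setting, 82 per arm:

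| Separation d (SD) | r from formula | Chance from formula | Simulated, no arm term | Simulated, with arm term |
|---|---|---|---|---|
| 0.5 | −0.053 | 10% | 10% | 5% |
| 1 | −0.098 | 24% | 24% | 5% |
| 2 | −0.154 | 51% | 51% | 5% |
| 3 | −0.182 | 65% | 65% | 5% |
| 4 | −0.195 | 72% | 71% | 5% |

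Nearly all the significant pooled slopes point in the hypothesised direction (more NO, less abnormality). The median odds ratio per within-arm SD is 0.78 to 0.89 without an arm term and about 1.00 with one.

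**5. Controls and sensitivity.**
- No marker shift (d = 0): 5.5%. No treatment effect (40% v 40%, d = 2): 4.4%. Both arm effects are needed for the artefact.
- Smaller treatment effect at d = 2: 15% for 40% v 30%, and 31% for 40% v 25%.
- Only 40 infants per arm with marker data: 13%, 27% and 35% at d = 1, 2 and 3.

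**6. What the adjusted analysis can detect.** Suppose instead that the whole 40% v 20% effect passes through the marker, measured without error, at 82 per arm. Power for the marker coefficient with an arm term, using both arms, is about 78% at d = 2 and 44% at d = 3. For the slope within the iNO arm alone it is about 39% and 19%.

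**The case against.** The strongest reply is that the plan is silent rather than wrong. Section (vii) speaks only of regression techniques. It does not say that there is one model, that the arms are pooled or that covariates are excluded, and the goal in (i) mentions administered concentrations, which separate iNO from placebo. A reader might infer that the plan expressly commits to an unadjusted pooled model; the documents do not support that. What stands is that pooling is the plain reading. Both arms are sampled, treatment group is assigned only to the comparison of means, and the stated goal about concentrations is never turned into a model.

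A reader might also infer that any benefit of iNO is bound to produce a positive Aim 2 result. It is not. The chance depends on an unknown separation, was 10% at 0.5 SD and never exceeded 71% in the settings tried, and falls with a smaller treatment effect or incomplete sampling. Incomplete sampling is plausible because the samples are leftovers from routine draws. The volunteer data concern total nitrosylated hemoglobin, not A-V differences in preterm infants.

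Nor is the analysis unable to address its own hypothesis. As worded, that hypothesis is a positive correlation, and a pooled regression does test it. What a pooled regression cannot do is support the mechanistic reading in the Aim's title.

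Finally, it is tempting to make the slope within the iNO arm the decisive test. Step 6 shows it would usually miss a true mechanism at 2 to 3 SD.

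**Conclusion.** The point holds as a gap in specification with a material consequence. Followed as written, the Aim 2 outcome analysis is a pooled regression whose slope includes the arm contrast, so it can be significant when NO delivery plays no part within either arm. At the design size and planned effect, this happens in about 10% to 65% of trials for separations of 0.5 to 3 SD, against about 5% with a treatment term.

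These rates assume a binary outcome, a normal marker with equal SD in both arms, complete marker data, a two-sided 5% test and the planned 40% v 20% effect. The separation is an assumption throughout. The primary Aim 1 comparison is not affected.

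**What to change.** In Specific Aim #2 (vii), specify that the outcome regressions for the A-V differences and for cGMP use infants from both arms and include treatment arm, gestational age and birth weight. State that the mechanism inference rests on the arm-adjusted marker coefficient. Report the pooled correlation and the arm-specific slopes as descriptive.

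The cost is a few sentences and model terms, with no new data: treatment arm and birth weight are recorded at randomization, and gestational age is needed to set treatment duration.

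There are two limits to state alongside. The adjusted slope is less precise (step 6), so a null result does not rule out the mechanism. An arm term removes the between-arm artefact but does not prove mediation, because illness severity may still affect both NO delivery and outcome within an arm.

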#### **EXPECTED IMPACT OF THE PROJECT.**

Although there is great interest in the neonatal community about our prior finding of improved neurodevelopmental outcome and growth among premature infants treated with nitric oxide (see attached newspaper articles), additional corroborative data from a study specifically designed to examine the effect of nitric oxide therapy on neurodevelopmental outcomes is required to change current recommendations for neonatal care. If supportive, this specifically designed project would provide that corroborative data, such that we and other authorities could recommend that routine care of premature infants include nitric oxide treatment for improved neurodevelopmental outcomes. Consequently, this project would be expected to provide a marked improvement in neurodevelopmental outcome for the thousands of preterm babies born in the US every year.

Principal Investigator: [name]

**PLANS FOR ACKNOWLEDGING FOUNDATION SUPPORT FOR THE PROJECT.**

All papers reporting data from this study will specifically acknowledge the support of the Gerber Foundation. The text will say: "Funded by a grant from the Gerber Foundation." Similarly, all talks, abstracts, and posters will contain specific acknowledgement.

## Appendices

### A. Project schedule/Timeline of events

Time	Project Stage	Activity
Year 1 month 1	Begin patient enrollment	randomize to NO or placebo
	Begin assessment of NO delivery and metabolism during hospitalization	measurement of arterial and venous nitrite and nitrosylated hemoglobin
year 1 month 3	anticipate 1st discharges to home - assess complications of prematurity potentially affecting neurodevelopmental outcome	Routine head ultrasounds Routine head MRI at discharge Classification of chronic lung disease
year 1 month 9	Interim safety analysis	Comparison of death rates and rates of Grade IV IVH between groups
Year 2 month 7	End patient enrollment	
	Begin assessment of 18 month neurodevelopmental outcome	Bayley scales Neurologic exam Assessment of CP status Assessment of Blindness Assessment of hearing
Year 2 month 7		
Year 3 month 12	End 18 month neurodevelopmental outcome assessment	

### B. Collaborations/Linkages.

An ongoing collaboration will be made with the University of Chicago Neonatal Follow-up Clinic in which our infants will be seen for routine follow-up and neurodevelopmental assessment. Particularly important, will be our collaborations with [name], our neurodevelopmental assessment specialist, who performs the Bayley developmental assessments on all our babies, as well as with our social work staff. Our social work staff's involvement with our subjects' families has been shown to be very helpful in keeping contact with them, and ensuring our very high follow-up rates in this economically depressed population.

Principal Investigator: [name]

